#### Session 2:

- 1. Neurodevelopment computer tests (see section 2.1.6) (25 minutes)
- 2. Hand out of all material (15 minutes) and explanation of each device and biological sample collection kits. List of material:
  - O URINE COLLECTION KIT:
    - 12 urine containers and a special box to maintain the temperature
    - Urine collection instructions and questionnaire (Annex 3)
  - STOOL COLLECTION KIT:
    - 1 collection tube for the stools.
    - Stool collection instructions and questionnaire (Annex 3)
  - MONITORING DEVICES (to be worn/carried during at least 7 consecutive days): Please note for the BiB cohort: we expect that some adolescents will require two subsequent Saturday appointments due to their school commitments. In order to achieve 7 full days of measuring, we will drop off the devices at the home address and explain via phone or, if requested, for example via ZOOM call.
    - Instructions (Annex 3)
    - A GENEActiv that the adolescent will wear to record physical activity and sleeping patterns (see section 2.1.8.1).
    - A smartphone with the ExpoApp3 installed, to be carried in a pouch provided by the fieldworkers, to record mobility (see section 2.1.8.2).
    - An Actigraph accelerometer that the adolescents will wear to record physical activity (only in a subsample) (see section 2.1.8.3).
    - A NO2 diffusion tube that will be placed on the outside of their backpack to measure the personal NO2 exposure levels (see section 2.1.8.4). If they do not want to carry it, we can offer the possibility of placing the NO2 in the living room.
    - Incidence form: to report any issues with devices

- SLEEP AND PHYSICAL ACTIVITY DIARY that the adolescent will fill in every day, during 7 consecutive days, when he/she wakes up and before going to sleep (see section 2.1.5.3).
- INFORMATION SHEET with a detailed explanation of what the adolescent has to do during the monitoring week.
- ADOLESCENT Food Frequency Questionnaire (FFQ) to be completed at home (see section 2.1.5.1)
- PARENTS QUESTIONNAIRE to be completed at home including the Child Behaviour Checklist (see section 2.1.5.1).

#### **Day 6: REMINDER**

Adolescents and their families will be contacted by phone to:

- Perform the parents' short questionnaire (phone interview)
- To remind them:
  - o To complete the questionnaires and bring them to the visit.
  - To collect stool samples on Day 6 or Day 5 To bring the urine and stool samples and the corresponding questionnaires
  - o To bring all the devices: GENEActiv, (Actigraph), NO2 diffusion tube and the corresponding incidences sheet.
  - o To bring the sleep and physical activity diary.
  - That the adolescent is required to FAST, consuming no food or liquids other than water, for at least 8 hours before the second visit to perform the blood drawn.

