#### IMPORTANT CONSIDERATIONS FOR THE ORGANIZATION OF THE FIELDWORK:

1. All HELIX children should be included in the visit (see Annex 29 for the list of IDs HELIX kids) — even if they do not want to do one part (e.g. blood, stools). The follow-up priorities are as follow:

	PRIORITIES (1= high priority to 4 = low priority)	
Clinical exam		
Anthropometry	1	
Blood pressure	1	The clinical outcomes (and outcome
BIA	1	questionnaires such as CBCL/SDQ, asthma/allergy) are our main
Spirometry	1 (if possible)	priority. The clinical visit is essential.
Neuro tests	1	
Devices		
GENEActive	3	
NO2 tubes	3	Monitoring can be left out if this
ЕхроАрр3	3	makes the difference between participation or not.
Actigraph	3	participation of float
Questionnaires		
qGIS	1	We need address data
Diary	3	If they do not do the monitoring devices (above), then this is not needed either
Adolescent main	1	
Adolescent FFQ	3	Can be done by parents
Adolescent puberty	2	
Parents phone	1	Parents' questionnaires should not be a problem (not important for
Parents home	1	convincing the kid)
Biological samples		

12 urines	2	Could be reduced if this makes the difference between participating or not
Blood	2	PaxGene optional
Feces	2	
Hair	Optional	

IMPORTANT NOTE: all the items above are important and all are included in the main protocol. Priorities should only be used if the adolescent would otherwise not participate at all. We can also ask if we can contact the family again next year if they do not want to do it now. We can ask the child which part he/she does not want to do.

- 2. Devices available per cohort (this allows to follow 6 children/week):
  - o 7 GENEActiv
  - o 7 Smartphone
  - o 1 Actigraph (for the validation of GENEActiv in a subsample)
- 3. The monitoring week starts on Day 1 and finishes on the day of blood drawn (see Table 3 below) and must include a minimum of 7 consecutive days (24-hours period).
- 4. The blood drawn MUST be performed at the end of the monitoring week (from Day 8 to Day 10 both included, see Table 3 below).
- 5. The blood drawn MUST be performed after a FASTING period of at least 8 hours (not eating or drinking, except water). ONLY in the EXCEPTIONAL CASE in which fasting blood cannot be collected due to fieldwork constraints, non-fasting blood will be collected ensuring at least 2 hours fasting time since the last meal.

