#### IMPORTANT CONSIDERATIONS FOR THE ORGANIZATION OF THE FIELDWORK:

- 1. All HELIX children should be included in the visit although they do not want to do one part (e.g. blood, stools) (see Annex 29).
- 2. Devices available per cohort:
  - o 7 GENEActiv
  - o 7 Smartphone
  - 1 Actigraph (for the validation of GENEActiv in a subsample)
- 3. The monitoring week should be of 7 consecutive days (24-hours period) minimum (Table 3).
- 4. The blood drawn should be performed at the end of the 7 days of the monitoring week
- 5. The blood drawn MUST be performed after a FASTING period of at least 8 hours (no eating or drinking, except water).
- 6. Blood MUST be processed within a maximum of 6 hours after collection (e.g. a blood sample collected at 8.00h should be processed before 14.00h).
- 7. The clinical examination and blood collection can be done in separate days.

**Table 3.** Flexibility of the visits: the clinical examination can be done within 0-15 days after the delivery of the devices and blood extraction can be done from day 8 to day 10.

	Day -7	Day -6	Day	Day 10	Day 11	Day 12	Day 13	Day 14	Day 15	Day 16	Day 17														
Hand out material	-/	-			,	_	_	х	_	-		-			,		_	20				24		20	
Monitoring									Х	Х	Х	Х	Х	х	Х	Х	Х	Х							
Blood drawn																Х	Х	Х							
Clinical examination	х	х	х	х	х	х	х	х	х	х	х	х	х	х	х	х	х	х	х	х	х	х	х	х	х

Considering the large number of tests, questionnaires, and devices that need to be completed and carried during 1 week, our suggestion is to organize the visit on two different days:

#### Option 1

- Visit 1 (Day 0): clinical examination and hand out of the material for the 7-days personal monitoring and the biological samples collection kits;
- Visit 2 (Day 8): blood collection early in the morning and collection of all the 7-days personal monitoring material, and stools and urines samples.

#### Option 2

- Visit 1 (Day 0): hand out of the material for the 7-day personal monitoring and the biological samples collection kits (this can be done at home, at the study centre, or sent it by postal mail);
- Visit 2 (Day 8): blood collection early in the morning followed by the clinical examination and collection of the 7-days personal monitoring material, and stools and urines samples.

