#### Day 6: Reminder

Adolescents and their families will be contacted by phone /test or WhatsApp to:

- Perform the parents' short questionnaire (can be phone interview)
- Remind them
  - To complete the questionnaires and bring them to the visit.
  - To collect stool samples on Day 7 or Day 6 in case they usually have constipation.
  - To bring the urine and stool samples and the corresponding questionnaires.
  - To bring all the devices: GENEActiv, (Actigraph), NO2 diffusion tube and the corresponding incidences sheet.
  - o To bring the sleep and physical activity diary.
  - The adolescent is required to FAST, consuming no food or liquids other than water, for at least 8 hours before the second visit to perform the blood drawn, and she/he should wear COMFORTABLE CLOTHES for the clinical examination.

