## 2.1.7 Biological sample collection

Table 5 shows the biological samples to be collected from each of the adolescents during this follow-up and their purposes:

- One hair lock will be collected by the fieldworkers after the clinical examination of the adolescent (in visit 1) following procedure in Annex 18.
- 12 urine samples (morning and night samples from 6 consecutive days) and 1 stool sample will be collected by the adolescent between visit 1 and 2. In visit 2, participants will bring them to the centre and the fieldworkers will store the urines in the fridge or the freezer depending if they are processed the same day or not (see Annex 21) (maximum 6 hours). Stool samples MUST be directly stored at -80°C.
- If adolescent does not bring the urine samples with them, a new sample will be collected at this point.
- Fasting blood will be collected by trained nurses (in visit 2)

**Table 5.** Biological samples to be collected in new follow-up of HELIX Subcohort

Type of sample	Tube/Bag	Sample processing	Sample quantity required	Purpose
Hair	Zip- lock bag	Hair	-	Reserve
Urine	Virtex Vacusence	Weekly pool (3	0.35 mL	Phthalates
	112510 plastic	aliquots)	0.5 mL	Phenols
	polypropylene		0.5 mL	OP pesticides
	70/10mL (collected at 12 time points)		0.5 mL  0.5 mL  0.5 mL	Other pesticides (metabolites of pyrethroids, 2,4- dichlorophenoxyacid, boscalid and imazalil)  Cotinine  Glycol ethers  Polycyclic aromatic hydrocarbon  Creatinine
			1.75 mL	Exogenous metabolomics
		1 aliquot of each urine + 6 aliquots of the weekly pool	1.8 mL x 18 aliquots	Reserve
Blood (19.5 mL)	6 mL silica (clot activator) vacutainer	Serum	0.5 mL	Endogenous metabolomics
	368815		0.25 mL	Glucose, total and HDL cholesterol, triglycerides, phospholipids, ALT, AST,

		,		GGT
			0.1 mL	Reserve - Antibodies against SARS-CoV-2 + inflammatory proteins
			0.45 mL	Reserve - IgEs
			<1 mL	Reserve
	5 mL silicone coated glass vacutainer	Serum	0.5 mL	Exogenous metabolomics
	367614		0.5 mL	Exogenous metabolomics
			<1.5 mL	Reserve
	6 mL K2EDTA (trace	Whole blood	0.9 mL	Metals and elements
	elemento determination)		0.5 mL	Reserve
	368381	Buffy coat	0.5 mL	Telomere length
		Plasma	0.2 mL	PFASs
			0.5 mL	Endogenous metabolomics
			<1 mL	Reserve
		Red cells	1.5 mL	Reserve
	2.5 mL PaxGene 762125 OPTIONAL	RNA	2.5 mL	Transcriptomics
Stool	1 Zymo tube R1101	Bacterial DNA	1 Zymo tube	Microbiome

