#### 2.1.7.3 Stool sample collection

A stool sample will be collected by the adolescent at home, preferably in the morning of the day before visit 2. The adolescent will bring the stool sample to the ATHLETE fieldworkers on visit 2. Stool samples will be collected for an accurate assessment of the gut microbiota. The protocol for collection of the stool samples by the adolescent can found in Annex 3, while the protocol on labelling, and storage of stool samples can be found in the Child Stools Collection SOP (Annex 22).

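### The Option 1 reminder, given on Day 6, asks for stool on Day 6 or Day 5, which conflicts with Option 2 and section 2.1.7.3 and names a day already past

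*Protocol*

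**What the plan says.** The protocol gives a day for the home stool sample in three places.

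- Section 2.1.3.1 (Option 1), Day 6 reminder: "To collect stool samples on Day 6 or Day 5".
- Section 2.1.3.2 (Option 2), Day 6 reminder: "To collect stool samples on Day 7 or Day 6 in case they usually have constipation".
- Section 2.1.7.3, which names no option: "preferably in the morning of the day before visit 2".

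Both options place visit 2 on the same day and collect the stool there. The fieldwork considerations in section 2.1.3 give, for Option 1, "Visit 2 (Day 8): blood collection early in the morning and collection of all the 7-days personal monitoring material, and stools and urines samples", and for Option 2, "Visit 2 (Day 8): blood collection early in the morning followed by the clinical examination and collection of the 7-days personal monitoring material". The blood draw, which defines visit 2, may take place "from Day 8 to Day 10 both included", and the Table 3 caption repeats that window.

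On receipt, section 2.1.7 requires: "Stool samples MUST be directly stored at -80°C". Section 2.1.3 also leaves the organisation of fieldwork to each cohort, according to its characteristics, resources and preferences.

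**The concern.** One sample has differing collection instructions, and the visit option decides which of them a family hears. One instruction cannot be followed in full: a call on Day 6 cannot prompt a collection on Day 5.

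The sample is for the gut microbiota. The instruction to freeze at once on receipt suggests that the sponsor regards time before freezing as relevant. Section 2 gives common data collection procedures as the main aim of the follow-up. If the collection day differs by option while hand-over stays at visit 2, the time a sample spends unfrozen also differs by option, through wording alone. A sample taken on the wrong day cannot be taken again retrospectively, so the instruction is better settled before collection than handled in analysis.

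**Working it through.** The plan states no figure for time before freezing, so there is none to reproduce. It follows from the days given.

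**Inputs**
- Collection day, Option 1: Day 6 or Day 5 (section 2.1.3.1, reminder).
- Collection day, Option 2: Day 7, or Day 6 as the constipation fallback (section 2.1.3.2, reminder).
- Collection day, section 2.1.7.3: visit 2 day minus 1, as a preference.
- Visit 2: Day 8 in both options, with Day 9 and Day 10 allowed (section 2.1.3 and Table 3).
- Hand-over and -80°C storage: at visit 2 (sections 2.1.7 and 2.1.7.3).

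**Formula.** Days before freezing = visit 2 day − collection day.

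**Nominal schedule, visit 2 on Day 8**
- Option 1: 8 − 6 = 2 and 8 − 5 = 3.
- Option 2: 8 − 7 = 1, and 8 − 6 = 2 with constipation.
- Section 2.1.7.3: 8 − 7 = 1.

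**If visit 2 moves and the day labels are kept**

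| Visit 2 | Option 1 | Option 2 (main; constipation) | Section 2.1.7.3 |
|---|---|---|---|
| Day 8 | 2 or 3 | 1; 2 | 1 |
| Day 9 | 3 or 4 | 2; 3 | 1 |
| Day 10 | 4 or 5 | 3; 4 | 1 |

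**What the comparison shows**
- Taking first-named day against first-named day and second against second, Option 1 is always one day longer than Option 2 (7 − 6 = 1; 6 − 5 = 1).
- Option 2's main rule agrees with section 2.1.7.3 when visit 2 is on Day 8. Option 1 agrees with section 2.1.7.3 on none of the permitted visit days: the day before is Day 7, 8 or 9, and Option 1 names only Days 5 and 6.
- The Option 1 call is on Day 6, so its Day 5 alternative passed one day earlier (6 − 5 = 1). Option 2's call, also on Day 6, names no day that has already gone.

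**The case against.** Several points on the other side are fair.

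- **The conflict is narrower than three incompatible rules.** On the nominal schedule Option 2's main rule and section 2.1.7.3 both give Day 7, and Option 2's Day 6 is only a fallback. The outlier is the Option 1 line. This stands.
- **Section 2.1.7.3 expresses a preference.** Its one-day figure is a target and not a guaranteed maximum. This stands, but a preference for the day before does not make Day 5 or 6 a suitable standard instruction.
- **The Option 1 line may have lost words.** In the text available it runs straight into the next reminder, and its Option 2 counterpart goes on to mention constipation. If Day 5 was also meant as a fallback, Option 1's main day would still be Day 6 against Day 7, and the fallback would still be past at the time of the call.
- **The longer figures are conditional.** The 4 and 5 days in the table require visit 2 to move to Day 10 while families keep to labels written for a Day 8 visit. Nothing says the labels stay fixed. A reader might infer a five-fold spread (5 days against 1) as a planned feature; the documents support only the Day 8 contrast without that assumption.
- **Alignment with cohort is not shown.** A reader might infer that storage time differs by cohort and so cannot be separated from cohort differences or exposures. Cohorts may choose their organisation, but no option is assigned to any cohort, and one cohort could use both. Visit day and the constipation fallback would also vary the lag within a cohort.
- **Harm to the microbiome data is not shown.** Table 5 names a Zymo tube without describing any preservative. Annex 3 (instructions given with the kit) and Annex 22 (labelling and storage) are not available here. They may bear on home storage, but they cannot remove a disagreement within the protocol text.

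**Conclusion.** The Option 1 stool instruction is wrong as written. It conflicts with the Option 2 reminder and with section 2.1.7.3, and one of its two days has passed when the reminder is given. No other part of the protocol resolves this.

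The size that can be stated is 2 to 3 days before -80°C storage under Option 1, against 1 day (2 with constipation) under Option 2 and about 1 day under section 2.1.7.3. It rests on visit 2 taking place on Day 8, families following the reminder, and the sample being frozen at visit 2. Longer times on Day 9 or 10 arise only if the day labels are kept.

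Alignment with cohort is a possibility, and bias in the microbiome results is not established. Whether an analysis should adjust for time before freezing is a matter for the analysis plan; its absence from the protocol is no fault. This is an internal inconsistency with a modest, avoidable effect on how uniformly samples are handled.

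**What to change.** Reconcile the reminders in sections 2.1.3.1 and 2.1.3.2 with section 2.1.7.3, and Annex 3 if it is affected, into one collection rule for both options. Express the rule as days before the actual visit 2 date, so that it still holds when the visit falls on Day 9 or 10, and say whether a fallback day exists and for whom. Give the reminder before the target collection day, including any fallback day. Which day to adopt is for the sponsor to settle.

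The cost is a wording change to two reminder texts, to section 2.1.7.3 if needed, and possibly to the instruction sheet, together with a possible shift in the date of the reminder call. No additional sample, visit or staff is needed.

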#### Day 8: VISIT 2 - BLOOD DRAWN

- 2 Time of the day: in the morning after minimum 8 hours fasting
- Duration: 75 minutes (15 min blood drawn + 15 min breakfast + 45 min questionnaire)
- Place: clinical research facility, home
  - Perform the **BLOOD DRAW** (15 minutes)
  - After the blood drawn, teenagers will be left for 15 minutes for breakfast and, if necessary, go to the toilet.
  - The nurses/fieldworkers will
    - Collect
      - the biological samples (12 urine samples and 1 stool sample), label them and ensure that the corresponding questionnaires are completed (Annexes 5 and 8).
      - the different devices and the corresponding incidence sheet.
      - the sleep and physical activity diary.
      - the adolescent's and parent's questionnaires
    - o Check that all questionnaires/forms are completed.
    - Store the blood samples in the fridge until processing (for a maximum of 6 hours).

#### Adolescent's main questionnaire (see section 2.1.5.1) (45 minutes)

The adolescent main questionnaire takes 45 minutes approximately. Record on the clinical data sheet if the adolescent answered the questionnaire alone or with help from fieldworkers (Annex 18). It should be answered by the adolescent alone, but fieldworkers should be available to answer questions the adolescent might have:

- to provide a specific timeframe to the adolescent to fill it in (to increase the completeness of the questionnaire)
- to ensure support from fieldworkers to the adolescent in case of doubts
- to guarantee a semi-private environment for the adolescent

#### 2.1.3.2 Option 2 - clinical examination and blood drawn on one day

Figure 3. Suggested organization of the visit on one day

Day 8: VISIT 2 - Blood Contact with Day 0: VISIT 1 - Hand out of drawn + Clinical material + Questionnaire families Day 6: Reminder examination Email/postal mail: 1. Informed consents signed Call (to remember): 1. Blood pressure Information sheet 2. Parents' phone questionnaire Questionnaires 2. Fasting blood drawn Informed consents complementation 3. Handout of material: 3. Breakfast Biological samples Description of the visit · Urine and stool collection kits 4. VISIT: Session 1: Clinical collection examination // Session 2: · Devices: GENEActiv, Smartphone, Bring all devices Neuro tests + Questionnaire Actigraph, diffusion tubes + Hair sample) · Empty stomach the day • Sleep and physical activity diary of the blood extraction 5. Collection: Adolescent FFQ and comfortable · Biological samples clothes Parents questionnaires Devices Ouestionnaires 6. Check questionnaires 7. Store the samples

#### **CONTACT WITH FAMILIES**

**First contact:** make the first contact with the families by phone and inform them about the new visit corresponding to the adolescence period.

#### Day 0: VISIT 1 - HAND OUT OF MATERIAL + ADOLESCENT'S QUESTIONNAIRE

- **Time of the day: not important**
- Duration: 75 mins (10 min visit description + 15 min hand out material + 45 min questionnaire)
- Place: clinical research facility, home

**Families can be visited at home or at the study centre.** If material is sent by postal mail, families will be telephoned.

It is PREFERABLE that the families are visited at home or at the study centre to:

- Ensure that the consent forms are signed before the start of the visit (Annexes 1-2);
- Have the adolescent answering the main questionnaire

If families are not visited they can send back the signed consent forms by postal mail.

NOTE: As COVID-19 pandemic are easing home visits may be carried out for example to collect consent or fasting bloods. The situation will be monitored closely and official and local guidelines followed

The following will be done during the family visit:

- Go over the information sheet, describe the whole visit, and answer possible questions that parents and the adolescent may have (10 minutes).
- Sign the **consent forms** (parents and adolescent) (Annexes 1 and 2).
- Hand out of all material (15 minutes): the personal exposure monitoring devices, the
  urine and stools collection kits, the diary, the information sheet and the incidences
  form are handed out to the adolescent following a detailed explanation about each
  one of them:
  - O URINE COLLECTION KIT:
    - o 12 urine containers and a special box to maintain the temperature
    - Urine collection instructions and questionnaire (Annex 3)
  - STOOL COLLECTION KIT:
    - o 1 collection tube for the stools.
    - Stool collection instructions and questionnaire (Annex 3)
  - DEVICES (to be worn/carried during at least 7 consecutive days):
    - Instructions (Annex 3)
    - A GENEActiv that the adolescent will wear to record physical activity and sleeping patterns (see section 2.1.8.1).
    - A smartphone with the ExpoApp3 installed, to be carried in a pouch provided by the fieldworkers (see section 2.1.8.2).
    - An Actigraph accelerometer that the adolescents will wear to record physical activity (only in a subsample) (see section 2.1.8.3).
    - $\circ$  A NO2 diffusion tube that will be placed on the outside of their backpack to measure the personal NO2 exposure levels (see section 2.1.8.4). If they do not want to carry it, we can offer the possibility of placing the NO2 in the living room.
  - SLEEP DIARY that the adolescent will fill in every day, during 7 consecutive days minimum, when he/she wakes up and before going to sleep (see section 2.1.5.3).
  - ADOLESCENTSQuestionnaires (via link or paper based) adolescent questionnaire, puberty questionnaire and FFQ to be completed at home or at study centre (see section 2.1.5.1)
  - PARENTS QUESTIONNAIRE Parents questionnaires to be completed at home or at study centre including the CBCL (see section 2.1.5.1).
- Adolescent's main questionnaire (see section 2.1.5.1) (45 minutes)

(Note: To be completed ONLY in the case the adolescents are seen at their home or at the study centre, otherwise should be completed during the visit on day 8, after the neuro tests)

The adolescent main questionnaire takes 45 min approximately. It should be answered by the adolescent alone, but fieldworkers should be available to answer questions the adolescent might have. Record on the clinical data sheet if the adolescent answered

the questionnaire alone or with help from fieldworkers. It MUST be answered when the fieldworkers visit the participant's at home or when the adolescent is at the study centre:

- to provide a specific timeframe to the adolescent to fill it in (to increase the completeness of the questionnaire)
- to ensure support from fieldworkers to the adolescent in case of doubts
- to guarantee a semi-private environment for the adolescent

